4.3 Exclusion Criteria

Subjects with any of the following will not be eligible for study participation:

- A. Age < 61 years
- B. Patients unable to provide informed consent for prospective arm
- C. Secondary AML (*documented* history of antecedent hematological disorder, e.g., myelodysplastic syndrome or therapy-related AML) or CML in blast crisis
- D. Patients receiving, received, or who will receive a FLT3 inhibitor
- E. Patients receiving, received, or who will receive an IDH1 or IDH2 inhibitor
- F. SCr greater than 2 mg/dL
- G. Karnofsky PS of 40 or less at study entry
- H. History of any other disease, metabolic dysfunction, physical examination finding, or clinical laboratory finding giving reasonable suspicion of a disease or condition that contraindicates the use of protocol therapy or that might affect the interpretation of the results of the study or that puts the subject at high risk for treatment complications, in the opinion of the treating physician
- I. Prisoners or subjects who are involuntarily incarcerated, or subjects who are compulsorily detained for treatment of either a psychiatric or physical illness

J. For historical arm, subjects will be excluded if adequate data is not available in electronic medical record (e.g., if patient was followed by their local oncologist between chemotherapy cycles and labs/transfusions/clinic notes, etc. are not available)

4.4 Inclusion of Women and Minorities

Both men and women and members of all races and ethnic groups are eligible for this trial.

5. REGISTRATION PROCEDURES

All subjects must be registered with the UF Health Cancer Center prior to participation in this trial and must meet all subject eligibility requirements and complete informed consent. All consented subjects must be entered into a secured electronic data base that is encrypted and password protected.

All eligible and enrolled subjects will receive a unique subject number. This number will be used to identify the subject throughout the study. Subjects withdrawn from the study will retain their subject number.

6. STUDY PROCEDURES

Written informed consent must be obtained prior to performing any study-specific evaluations or tests. Tests or evaluations performed as standard of care within the specified screening period, but prior to informed consent, may be accepted for this study and need not be repeated. Screening measurements below will be obtained within 60 days prior to registration into the study. **After registering a subject into this study, study treatment must begin within 30 days or subject will need to be re-screened:**

- Demographic data, including date of birth, gender, race, ethnicity and zip code
- Medical history, including h/o MDS or other conditions that could cause secondary or treatment-related AML or other conditions that may have major psychiatric or medical illness(es) that may impact if subject able to consent or be monitored for cerebellar toxicity
- Previous diagnostic assessments and treatment(s) for AML including regimens and dates
- Medications that may exclude subject (such as FLT3 inhibitors, e.g. midostaurin, sorafenib, gilteritinib, or any investigational FLT3 inhibitor as well as IDH1 and IDH2 inhibitors, e.g., ivosidenib, enasidenib or any investigational IDH inhibitor
- Bone marrow aspirate and/or biopsy for clinical classification, flow cytometry, cytogenetic classification, molecular markers, NGS for identification of commonly tested mutations in AML at diagnosis and at hematologic recovery after induction chemotherapy

- Hematology laboratory evaluations:
 - Complete blood count (CBC) including hemoglobin, hematocrit, white blood cell (WBC) absolute with differential, and platelet count
- Blood chemistry laboratory evaluations: serum creatinine
- Blood transfusions, growth factors, anti-infective medications, eye drops

6.1 Schedule of Events

Visit: Procedure:	SCREENING (≤ 60 days prior to Day 1)	CYCLE 1		CYCLES 2 TO 4 IF SUBJECT CONTINUES		END OF TREATMENT ⁸ (+/- 14 DAYS)	FOLLOW UP (UP TO 48 MONTHS AFTER START OF INDUCTION) ⁹ EVERY 3 MONTHS (+/- 28 DAYS)
		Day 1	At each clinic visit per SOC (as clinically indicated ideally q48h+/- 24h)	Day 1	At each clinic visit per SOC (as clinically indicated ideally q48h+/- 24h)		
Informed Consent	X						
Demographic Information	X						
Medical and Cancer Treatment History ¹	X						
Medication History ²	X						
Bone Marrow Biopsy and/or Aspirate ³	X					As clinically indicated	
Interval History/Physical Exam ¹⁰	X	X	PRN SOC	X	PRN SOC	PRN SOC	
Karnofsky Performance Status ⁴		X					
BSA Used for Chemotherapy		X		X			
Vital Signs	X	X	PRN SOC	X	PRN SOC	X	
Pharmacogenomic Sample Collection		X					
Blood Chemistry Evaluations ⁵	X	X (+/- 72 HOURS AS SOC)	PRN SOC	X (+/- 72 HOURS AS SOC)	PRN SOC	PRN SOC	
CBC w/Diff	X	X (+/- 72 HOURS AS SOC)	PRN SOC	X (+/- 72 HOURS AS SOC)	PRN SOC	PRN SOC	
Administration of Blood and Platelet Transfusions		PRN SOC	PRN SOC	PRN SOC	PRN SOC	PRN SOC	
Administer Cytarabine Inpatient (q12h Days 1-3)		X		X			
Concomitant Medication Review ⁶		PRN SOC	PRN SOC	PRN SOC	PRN SOC	PRN SOC	

Adverse Event Review/Toxicity Assessment ⁷		PRN SOC					
RR and Survival Status (LFS and OS)						X	X
1) The bone marrow assessment, cytogenetics NGS, and/or molecular markers at diagnosis will be documented.							
2) Document specific medications that may exclude patient that have been taken during the 30 days prior to screening.							
3) The screening bone marrow assessment must be performed within 30 days after start of induction therapy, and must be reviewed at UF. This must confirm a diagnosis of AML, non-M3 in CR1 (less than 5% blasts on BM biopsy when ANC >1000 and platelets greater than 100). Results will be recorded, including cytogenetics and NGS and/or molecular markers.							
4) Performance status will be collected on Day 1 of Cycle 1; however, if this is not documented on this admission progress note, the last documented value within the screening periods will be used for baseline Karnofsky performance status.							
5) Blood chemistries including blood urea nitrogen, creatinine, alkaline phosphatase, AST, ALT, total bilirubin							
6) Document supportive care medications (pegfilgrastim or equivalent 48 hours +/- 24 hours after chemo ends; antimicrobial prophylaxis when neutropenic and other anti-infectives needed, eye drops until 48 hours after cytarabine ends, etc.) Supportive care medications and blood transfusions should be documented throughout and for 28 days after last treatment.							
7) Monitoring for SAEs at the time of consent and AEs collection will start the day patient starts cycle 1 of consolidation chemotherapy and continuing throughout the study. Subjects who have received at least one dose of study drug and discontinue prematurely (regardless of reason) will be monitored for any adverse events that occur during study until 28 days following the most recent dose of study treatment or initiation of a new chemotherapy regimen (whichever comes first). If a SAE or AE that is deemed related to the study intervention and ongoing at the end of the monitoring period the event will be monitored until resolution, event returns to baseline or in the investigator's opinion, deems the event is unlikely to resolve due to the patients underlying disease.							
8) End of treatment visit will occur in subjects who complete 3-4 cycles of consolidation or at study withdrawal (for example, at HCT conditioning, relapsed disease or if ended earlier than planned due to toxicity or physician discretion). Other assessments will be performed as necessary by the treating physician. Outside lab results may be collected if subject unavailable to travel to the institution.							
9) All subjects will be followed for long term outcomes until: relapse, death, or until closure of study.							
10) This data may be collected via telephone interview.							
Abbreviations: SOC= standard of care; PRN = as needed; BSA = OS = overall survival; SAE = severe adverse effects, AEs = adverse effects; HCT = hematopoietic stem cell transplant							

6.2 End of Treatment Evaluations

The End of Treatment date will be the date the subject has met one of the following:

- 3-4 cycles of planned consolidation treatment
- Study withdrawal
- HCT conditioning
- Treatment ended earlier than planned (due to toxicity or physician discretion)
- Relapsed disease

All subjects will have the following procedures documented:

- Reason for end of treatment (relapse or transplant, etc.)
- Supportive care medications and transfusions if needed
- AE assessment
- Hematology laboratory evaluations (unless recovery was documented in a previous visit): complete blood count (CBC) including hemoglobin, hematocrit, white blood cell (WBC) including differential and platelet count
- Assessed for complete hematologic recovery
 - Reference Appendix C. ELN Guidelines

6.3 Follow up Evaluations

Subjects will have follow-up visits for the evaluation of adverse events, labs, etc. per standard of care (after discharge from chemotherapy administration, generally every 48 hours +/- 24 hours until neutrophil and platelet recovery after each consolidation chemotherapy cycle). Patients will be evaluated prior to starting next chemotherapy cycle, then admitted for chemotherapy and monitored while inpatient.

If the subject is unavailable to travel to the institution (if situation changes from study inclusion criteria after subject starts first consolidation cycle), the visit may be made via telephone interview to review for adverse event resolution or the occurrence of any new adverse events, and outside labs reviewed if collected. Additionally, medical records may be requested with permission of the subject to complete remote visit reporting e.g., if admitted to an outside institution due to complications of chemotherapy.

If the subject is at the treating facility and the physician decides to hold, reduce, or omit the dose completely, the following procedures should be performed:

- Document reason for delay, decreased or missed doses
- AE assessment
- Hematology laboratory evaluations: complete blood count (CBC) including hemoglobin, hematocrit, white blood cell (WBC) with differential and platelet count

If study therapy is discontinued before planned, disease assessments will be performed as clinically indicated, such as suspicion of relapse. Reason for discontinuation should be documented, e.g., relapse, proceeding to HCT, unexpected toxicity/poor tolerance of chemotherapy, etc. Subjects will continue to be followed every 3 months (\pm 28 days) for survival data up to 48 months after induction chemotherapy is started, or until relapse or death (whichever comes first). Following discontinuation of study therapy for any reason, report the date as appropriate (date of confirmed relapse, date of death, date of start of HCT conditioning, or recovery from last planned or unplanned cycle).

If a subject becomes unreachable during the course of the study, the investigator or study team will make a reasonable effort to contact the subject and document each attempt. If these attempts are not successful, the subject may be declared "lost to follow up." For subjects lost to follow-up, the termination date will be the date of last contact with the subject.

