2.3.2 Exploratory endpoints

- Record pharmacogenomic profiles if results available from next generation sequencing (NGS)/GatorSeq on bone marrow (BM) biopsies for both arms (collected at diagnosis as standard of care).
- Compute ACSS SNP score using the genotype data for subjects in HiDAC 123 arm. We will genotype SNPs of relevance and based on the ACSS score classify into two groups having ACSS score ≥ 0 or <0 . ACSS score will be evaluated for association with certain endpoints (duration of neutropenia, thrombocytopenia, RR and OS). Peripheral blood samples will be collected and analyzed through [name] lab at the University of Florida and NGS results will be used to calculate the ACSS score.
- Describe relapse rate (RR). Relapse rate defined as incidence of confirmed relapse by peripheral blood flow or bone marrow biopsy results. Patients will be monitored up to 48 months after starting induction and will be reported if available.
- Describe overall survival (OS) and leukemia-free survival (LFS). Overall survival defined as the time from date of complete remission (CR) to death from any cause. Leukemia-free survival defined as time from CR to AML relapse or death, whichever comes first. Cause of death will be recorded. Patients will be monitored up to 48 months after starting induction and will be reported if available. These are not expected to be different between the two cohorts.^{1,2}
- Examine minimal residual disease (MRD) positivity after recovery from induction prior to study entry. The following modalities on bone marrow biopsy and aspirate will be used: flow cytometry (FC), karyotyping utilizing cytogenetics (CG), and fluorescence in situ hybridization (FISH). Patients with evidence of disease by any technique above will be classified as being MRD_{pos}. FC will be performed on bone marrow specimens using monoclonal antibodies either as a large panel if the patient was newly evaluated or as a limited but targeted panel based on previously known patient-specific leukemia immune phenotype. MRD will be reported as a percentage of CD45 positive white blood cells (WBCs) and will be labeled MRD_{pos} if leukemic cells account for $\geq 0.1\%$ of the analyzed total WBCs. CG will be performed using standard G-banding methods on 20 metaphase cells. FISH will be reported as a percentage of abnormal nuclei among the examined 300 interphase nuclei. MRD_{pos} by CG will be defined as abnormal karyotype seen in at least

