3. STUDY DESIGN

3.1 Study Overview

This is a single center, open-label, non-randomized phase II study. Twenty nine (29) subjects are planned to be enrolled in this study. Each subject will be administered cytarabine 1000 mg/m² IV q12h x 6 doses on Days 1-3 in the hospital during the consolidation treatment phase. Subject may receive up to four consolidation cycles. Subjects will have laboratory and toxicity assessments as clinically indicated (at baseline, then daily while inpatient and ideally every 48 hours after hospital discharge +/- 24 hours until count recovery from each cycle). These subjects will be compared to 29 historical controls [matched by age (within 3 years), gender (male or female), PS (Karnofsky: 90-100, 70-80, or 50-60) and number of HiDAC cycles received] who received HiDAC 135 from the time period of 2/1/2017-2/1/2019.

Screening data will be reviewed to determine subject eligibility. Subjects who meet all inclusion criteria and none of the exclusion criteria and who have consented will be entered into the study. The following treatment regimen will be used for prospective arm: cytarabine 1000mg/m² IV q12h x 6 doses (Days 1-3) for up to four cycles.

Historical arm subjects will have received cytarabine 1000 mg/m² IV q12h x 6 doses (Days 1, 3, and 5) for up to four cycles from the time period of 2/1/2017-2/1/2019.

Total duration of subject participation will be up to six months from start of first consolidation cycle (each cycle is 28 days, but more time may be required allowing extra time for delayed count recovery in some patients); study participation will end when subject recovers neutrophils and platelets after last administered cycle of chemotherapy, is admitted for conditioning chemotherapy for HCT, dies, or withdraws consent (whichever comes first). However, subjects will be followed every 3 months (\pm 28 days) for up to 48 months after start of induction to determine long-term outcomes. Total duration of the study is expected to be 60 months.

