8.2 Criteria for Study Treatment Discontinuation

Subjects who discontinue participation in the clinical study on their own or subjects who are withdrawn by the investigator, for reasons other than completion of treatment, proceeding to HCT, relapse or toxicity, will be defined as premature withdrawals. The end of treatment data will be collected if available at last visit if confirmed relapse, death, or proceeding to HCT. For those with toxicity that end before planned last cycle, data will be collected up to the end of treatment date and AE data will be collected until 28 days following the most recent dose of study treatment or initiation of a new chemotherapy regimen (whichever comes first).

Subjects will be followed for long term data every 3 months (\pm 28 days) until relapse, death or until 48 months after induction therapy (whichever comes first).

A subject will be discontinued from protocol therapy under the following circumstances:

- Any adverse event which, in the Investigator's opinion, requires termination of the chemotherapy
- Disease relapse
- If subject proceeds to allogeneic HCT
- The subject uses illicit drugs or other substances, or takes part in activities that may, in the opinion of the Investigator, have a reasonable chance of contributing to toxicity or otherwise interfering with results
- The subject is lost to follow-up
- Death
- Development of an intercurrent illness or situation which would, in the judgment of the investigator, affect assessments of clinical status and study endpoints to a significant degree

The Investigator will make every reasonable effort to keep each subject in the study unless it is in the subject's best interests to discontinue participation. If a subject is removed from the study or declines further participation, all EOT evaluations should be performed if the subject is willing and able to be assessed. A description of the reason(s) for withdrawal from the study must be recorded on the case report form (CRF). The Investigator should also ensure that all subjects are followed up for survival status after the Final Visit.

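### Three passages end long-term follow-up at relapse although overall survival counts death from any cause; if the stop is applied, exploratory OS is biased upward

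*Combined protocol and SAP*

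**What the plan says.** Section 2.3.2 sets the endpoint: "Overall survival defined as the time from date of complete remission (CR) to death from any cause". Relapse is an event for LFS, not for OS.

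Three places end long-term follow-up at relapse:

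- Section 6.3, expressly for survival data: "for survival data up to 48 months after induction chemotherapy is started, or until relapse or death (whichever comes first".
- Section 6.1, Schedule of Events, footnote 9: "All subjects will be followed for long term outcomes until: relapse, death, or until closure of study".
- Section 8.2: "until relapse, death or until 48 months after induction therapy (whichever comes first".

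Other places carry follow-up without naming relapse as a stop:

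- Section 8.2 again: "The Investigator should also ensure that all subjects are followed up for survival status after the Final Visit".
- Section 3.1: "for up to 48 months after start of induction to determine long-term outcomes".
- Section 2.3.2: "Cause of death will be recorded. Patients will be monitored up to 48 months after starting induction and will be reported if available".
- The schedule row "RR and Survival Status (LFS and OS" is marked in the follow-up column, which runs to 48 months. That column heading carries footnote 9.

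On use of the data, section 2.3.1 has OS described in each cohort and section 12.5 makes exploratory endpoints descriptive. Section 9.2 plans a Cox regression of OS by ACSS group. Section 2.3.2 adds that OS and LFS are not expected to differ between the cohorts.

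**The concern.** Stopping at relapse suits LFS but not OS. A subject who relapses and later dies has had an OS event. If contact ends at relapse, that death is never recorded and the subject is censored when the risk of death has just risen. This is informative censoring, and Kaplan-Meier and Cox methods both assume it away. With no tracing after relapse, the curve labelled OS shows only death without relapse.

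Two uses of OS are exposed. The ACSS Cox model would lose its post-relapse deaths. The cohort descriptions could also be measured differently, because no passage states a vital-status rule for the historical controls. If their charts include deaths after relapse and the prospective arm's data do not, the difference would favour HiDAC 123.

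**Working it through.** **Reading the passages together.** Footnote 9 and the 8.2 sentence apply the stop to subjects generally. The 6.3 sentence follows text on early discontinuation but names survival data. The other 8.2 sentence covers all subjects and has no stop at relapse, so section 8.2 conflicts with itself. Section 6.3 dates subjects lost to follow-up at last contact, but no passage says how OS is censored after relapse.

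**Size.** The documents give no relapse or death rates and no OS figure to reproduce, so every input here is an assumption, apart from the 29 subjects planned for the arm. The model has constant hazards: *r* for relapse, *d* for death without relapse, *p* for death after relapse. The horizon is *t* = 24 months.

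- *r* = ln 2 / median time to relapse (12, 24, 36 or 60 months)
- *p* = ln 2 / median survival after relapse (6, 12 or 24 months)
- *d* = −ln(1 − q) / 24, where q is 24-month death without relapse (0.05, 0.10 or 0.20)

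This gives 4 × 3 × 3 = 36 scenarios.

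True OS(t) = e^(−(r+d)t) + [r / (r + d − p)] × [e^(−pt) − e^(−(r+d)t)].

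OS censored at relapse, none traced = e^(−dt) = 1 − q at 24 months.

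*Largest gap (12 months, 6 months, 0.05).* r = 0.05776, p = 0.11552, d = 0.00214. Then e^(−(r+d)t) = 0.25 × 0.95 = 0.2375 and e^(−pt) = 0.0625. True OS = 0.2375 + (−1.0385)(0.0625 − 0.2375) = 0.419, against 0.95: +53.1 points.

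*Smallest gap (60 months, 24 months, 0.20).* r = 0.01155, p = 0.02888, d = 0.00930. Then e^(−(r+d)t) = 0.7579 × 0.80 = 0.6063 and e^(−pt) = 0.50. True OS = 0.6063 + (−1.4385)(0.50 − 0.6063) = 0.759, against 0.80: +4.1 points.

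**Partial tracing.** If a random fraction *f* of relapsed subjects is traced, the hazard the analysis sees is (d·S₀ + p·f·S₁) / (S₀ + f·S₁). Here S₀ and S₁ are the probabilities of being alive in remission and alive after relapse. Integrating this over 24 months gives:

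| Relapsed subjects traced | Overstatement of 24-month OS, points | Middle of 36 scenarios |
|---|---|---|
| None | 4.1 to 53.1 | 16.1 |
| Half | 1.9 to 16.0 | 6.7 |
| Three quarters | 0.9 to 6.6 | 3.1 |
| All | 0 | 0 |

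**Deaths by 24 months in 29 subjects.** All deaths = 29 × (1 − true OS); deaths without relapse = 29 × [d / (r+d)] × (1 − e^(−(r+d)t)). Over the grid:

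- all deaths: 3.3 to 18.4
- deaths without relapse: 0.8 to 5.1
- deaths after relapse: 1.9 to 16.1, or 27% to 95% of all deaths

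With none traced, the ACSS Cox model would see about 1 to 5 deaths instead of about 3 to 18.

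**Check with other assumptions.** With 24-month net relapse of 40–75%, net death without relapse of 10–20% and median survival after relapse of 4–24 months, the overstatement at 24 months is +7 to +57 points. It is positive in every scenario. When the death hazards before and after relapse are set equal it vanishes: both estimates are 65.2% at 46 months.

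**The case against.** The strongest reply is that little rests on OS. It is exploratory and descriptive, the synopsis limits the comparison with historical controls to the primary and secondary objectives, and section 2.3.2 already reports these data only if available. The expectation of no difference is not a test. The ACSS analysis depends on funding (section 9.3) and would have few events even with complete follow-up. All of that stands, and it limits the weight of the point. It does not remove the bias in the OS that would be described: a gap triggered by relapse is not a random gap.

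A second reply is that the contradiction is narrower than it looks. A limit of up to 48 months is a maximum and can coexist with an earlier stop, and the schedule column carries footnote 9. That is fair: sections 3.1 and 2.3.2 are silent on relapse rather than opposed to it. The direct conflicts are inside section 8.2 and between the three stops and the OS definition.

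A third reply is that the size comes from a chosen grid. That is also fair. The middle value is not an estimate, and the worst case needs zero tracing. The direction does not depend on the grid; it needs only a higher risk of death after relapse than in remission.

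Finally, section 7.3.5 removes subjects from the study at transplant conditioning. Section 3.1 ends participation at the same point but continues three-monthly follow-up, so follow-up after transplant is already intended. The wording should still be aligned.

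**Conclusion.** The concern holds. As written, three passages stop the follow-up that OS needs, one sentence of section 8.2 says otherwise, and no OS censoring rule settles it. The bias is conditional: it arises only for relapsed subjects whose vital status is not traced. On the assumed rates it is 4 to 53 points of 24-month OS with no tracing, 2 to 16 with half traced, 1 to 7 with three quarters traced, and none with full tracing. These figures illustrate the possible size and are not predictions. Any distortion between cohorts depends further on how control deaths are abstracted, which the documents do not say. The primary endpoint, LFS, relapse rate, power and sample size are untouched. The point should be corrected, because deaths that are not recorded may be hard to recover later.

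**What to change.** In footnote 9 of the Schedule of Events, section 6.3 and section 8.2, replace the stop at relapse with wording such as: *vital status is followed until death or 48 months from the start of induction (or study closure if earlier), including after relapse and HCT; relapse ends LFS follow-up only.* Align section 7.3.5 so that removal at conditioning does not end vital-status follow-up.

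State that OS is censored at the date last known alive, not at relapse. Apply the same vital-status rule to the historical controls, and report for each cohort how many relapsed subjects have unknown vital status.

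The cost is an amendment with IRB approval, three-monthly chart or telephone checks after relapse in up to 29 prospective subjects, and the same look-up for the controls. The consent pages are not in the reviewed text, so the sponsor should confirm that consent covers contact after relapse. The sample size does not change.
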